15.2.6.1 Overdose

Overdose of the investigational product will be considered an SAE, even when there are no symptoms or additional AEs, and will be reported according to the guidelines in Section 15.2.5. An overdose associated with symptoms must be reported as an AE.

15.2.6.2 Suicidal Ideation and Clinical Management

The documentation and proper management of suicidal ideation by sites will be documented with the use of the C-SSRS, completed by site clinicians during all visits. Safety will be evaluated throughout the course of the study.

Any patient who, based on the investigator's judgment, poses an imminent risk of suicide should be discontinued from the study. Suicide risk is assessed by the clinician at every visit.

Suicide, self-harm, and attempted suicide, irrespective of the method, will be reported as AEs (all suicides are SAEs; attempted suicides are considered to be SAEs). The event will be identified as suicide or attempted suicide, and the method of the suicide or attempt will be provided. If an attempted suicide meets the criteria for an SAE, the event must be reported according to the guidelines in Sections 15.2.4. If a suicide attempt does not meet the criteria for an SAE, it will be considered a reportable AE, and a Suicidal Ideation or behavior Reportable Event Form will be completed by the investigator and submitted in accordance with the SAE reporting procedure in Section 15.2.5.

15.2.6.3 Pregnancy

If a patient (or patient's partner) becomes pregnant during the study, it must be reported within 24 business hours of the time the investigator becomes aware of the event and in accordance with the procedures described on the Pregnancy Report Form. Although pregnancy itself is not regarded as an SAE/AE, unless there is a suspicion that a study drug may have interfered with the effectiveness of a contraceptive medication, the pregnancy details will be captured in the AE/SAE module of the eCRF. Any pregnancy that occurs from Visit 1 to 30 days following the last dose given will be followed for gestational outcome, and the outcome will be reported to the sponsor. The female patient will be discontinued from investigational product, but will continue to attend study visits for the duration of her participation in the study.

15.3 Concomitant Medications, Therapies, and Alcohol Restrictions

15.3.1 Concomitant Medications

Lurasidone is contraindicated with the use of strong CYP3A4 inhibitors (e.g., ketoconazole) and strong CYP3A4 inducers (e.g., rifampin) (see Appendix 1). The lurasidone dose should not exceed 40 mg/day if co-administered with moderate CYP3A4 inhibitors. There are no known reported interactions between DCS and lurasidone.

It is anticipated that participants entering the study will be receiving concurrent disorder-directed treatment with various combinations of medications, including:

 Approved antidepressants (e.g., SSRIs, SNRIs, TeCAs, fluoxetine), but not 5-HT-2A antagonists (lurasidone, aripiprazole, olanzapine/fluoxetine, quetiapine, cariprazine, or lumateperone) • Mood stabilizers (e.g., lithium, valproic acid, and lamotrigine)

Participants will be permitted into the study if they are treated with no more than one drug from each category of the indicated classes. Approved antidepressants and mood stabilizers will be maintained at stable dosages throughout the study. This is both to ensure continued treatment and to prevent withdrawal symptoms that may occur if such drugs are rapidly discontinued. Participants—taking aripiprazole, risperidone, brexpiprazole, lumateperone, olanzapine, cariprazine, or quetiapine will discontinue these medications prior to Randomization in order to avoid overlap with lurasidone.

Allowed concomitant medications include any prescription or over-the-counter medication not specifically excluded by the protocol (see Appendix 1), as well as stable, ongoing antidepressant or mood stabilizer therapy and stable allowed hypnotic therapy. Participants requiring excluded medications will be discontinued from the study and an Early Termination Visit will be performed in accordance with Section 9.1.3.

Prohibited concomitant medications that the patient and the investigator agree to discontinue for the purpose of study entry will be washed out for a period defined by the Investigator in consultation with the Medical Monitor. In the event concomitant medication washout is appropriate for a patient per investigator judgment, the patient must sign the informed consent form prior to beginning the washout period. Clinically appropriate tapering regimens should be used, if applicable. The Screening period may be extended, upon consultation with the Medical Monitor, to allow for a sufficient washout period.

All concomitant medications taken during the study and 4-weeks prior to study entry will be recorded in the electronic case report form (eCRF) for each patient, along with dosage information and start and stop dates.

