6.6 Dose Selection

Lurasidone is an FDA-approved medication for depressive episodes associated with Bipolar I Disorder (bipolar depression) as monotherapy and as adjunctive therapy with lithium or valproate at doses of 20 mg to 120 mg daily. The target dose of 66 mg/day is based on the mean daily dose

of lurasidone observed during the fixed titration phase of the lurasidone registration trial for its indication in bipolar depression (Loebel et al., 2014b) and further validated in the STABIL-B trial (Javitt, et. al. 2018). Up-titrations are permitted if needed to doses of 99 or 132 mg/day, and down-titrations are permitted to 33 or 49.5 mg/day, which span the range of doses used in clinical studies of lurasidone (Loebel et al., 2014a; Loebel et al., 2014b).

DCS is well tolerated as a second-line treatment for TB at therapeutic split daily oral doses in the range of 500 to 1000 mg/day. Based on prior clinical results and animal studies, it is anticipated that therapeutic effects of DCS will be associated with plasma doses in excess of 25 μ g/mL, which in turn are generally associated with daily oral doses in excess of 10 mg/kg (i.e., 700 mg/day for a 70 kg) individual. A starting daily dose at 700 mg DCS and 33 mg lurasidone will be used, and then titrated over 2 days to the target dose of 950 mg DCS and 66 mg lurasidone. Down-titrations of DCS to 825 or 700 mg/day are available in the case of side effects to permit reduced dosing within the anticipated therapeutic range (700 – 950 mg/day). The maximum dose of 950 mg/day is within FDA-approved dosing limits for DCS.

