9.1.3 Early Termination Visit

Every effort will be made to keep the participants in the study for the full study period. However, if a patient decides to discontinue the investigational product, the patient will be asked about the reason(s) for discontinuation and the presence of any AEs. If possible, the patient will be asked to complete the Day 42/Early Termination (ET) visit prior to discontinuation, and day 70 to assess safety. Following completion of the Early Termination Visit, the patient will either be treated by the investigator with standard of care or, should the patient choose, return to treatment by a prior/referring physician. In this case, the investigator will facilitate and coordinate follow-up to ensure continuity of care.

Participants who discontinue from the study will not be replaced.

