10.3 Investigational Product Titration

Investigators will have the ability to increase the lurasidone dose at any point after the initial titration period for control of agitation or psychotic symptoms, or to decrease both the DCS and lurasidone dose in response to somnolence. No other dose modifications will be allowed.

Titrations of investigational product will be affected while maintaining a blinded study design (see Table 2 for NRX-101 and Table 3 for lurasidone). Up-titration will increase the lurasidone dose, and will not alter the DCS dose. Down-titration decreases the total daily dose of both lurasidone and DCS in the NRX-101 group and only the lurasidone dose in the lurasidone group.

Table 2 NRX-101 Dose Titration

	Morning Dose (mg)		Evening Dose (mg)		Total Daily Dose (mg)	
Day	DCS	Lurasidone	DCS	Lurasidone	DCS	Lurasidone
1	350	16.5	350	16.5	700	33
2	475	33	475	33	950	66
3	475	33	475	33	950	66
4	475	33	475	33	950	66
5	475	33	475	33	950	66
Maintenance Dose	475	33	475	33	950	66
Up-titration (if needed)						
step 1	475	33	475	66	950	99
step 2	475	66	475	66	950	132
Down-titration (if needed)						
step 1	350	16.5	475	33	825	49.5
step 2	350	16.5	350	16.5	700	33

Table 3 Lurasidone Dose Titration

	Morning	Morning Dose (mg)		Evening Dose (mg)		y Dose (mg)
Day	DCS	Lurasidone	DCS	Lurasidone	DCS	Lurasidone
1	0 (placebo)	16.5	0 (placebo)	16.5	0 (placebo)	33
2	0 (placebo)	33	0 (placebo)	33	0 (placebo)	66
3	0 (placebo)	33	0 (placebo)	33	0 (placebo)	66
4	0 (placebo)	33	0 (placebo)	33	0 (placebo)	66
5	0 (placebo)	33	0 (placebo)	33	0 (placebo)	66
Maintenance Dose	0 (placebo)	33	0 (placebo)	33	0 (placebo)	66
Up-titration (if needed)						
step 1	0 (placebo)	33	0 (placebo)	66	0 (placebo)	99
step 2	0 (placebo)	66	0 (placebo)	66	0 (placebo)	132
Down-titration (if needed)						
step 1	0 (placebo)	16.5	0 (placebo)	33	0 (placebo)	49.5
step 2	0 (placebo)	16.5	0 (placebo)	16.5	0 (placebo)	33

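### The protocol's 40 mg/day lurasidone limit with moderate CYP3A4 inhibitors cannot be kept at the 66 mg/day study dose, and no rule bars these inhibitors as a class

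*Protocol*

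**What the plan says.** **The limit.** Protocol 15.3.1, repeated in SAP 12.3.1, treats strong CYP3A4 inhibitors and inducers as contraindicated and points to Appendix 1 for them. For moderate inhibitors it gives a dose limit with no cross-reference: "The lurasidone dose should not exceed 40 mg/day if co-administered with moderate CYP3A4 inhibitors".

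**The dose.** Protocol Tables 2 and 3 give both arms 33 mg lurasidone on Day 1 and 66 mg/day from Day 2. The synopsis keeps 66 mg/day as maintenance through Day 42.

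**Permitted dose changes.** Protocol 10.3 lets investigators raise lurasidone for agitation or psychotic symptoms, or "decrease both the DCS and lurasidone dose in response to somnolence. No other dose modifications will be allowed". A step down lowers "both lurasidone and DCS in the NRX-101 group and only the lurasidone dose in the lurasidone group". Protocol 6.6 is somewhat wider: "Down-titrations of DCS to 825 or 700 mg/day are available in the case of side effects". Neither section lists a drug interaction as a reason.

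**Concomitant drugs.** The default in 15.3.1 is permissive: "Allowed concomitant medications include any prescription or over-the-counter medication not specifically excluded by the protocol". Exclusion criterion 20 only refers to Appendix 1, which works mainly by naming drugs within therapeutic classes and has no row for moderate CYP3A4 inhibitors.

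**The concern.** A site that follows the dosing schedule, the titration rule and the concomitant-drug rule exactly as written can still put a participant above the protocol's own drug-interaction limit. It also cannot apply the limit by lowering the dose, because 10.3 does not permit a decrease for that reason. What is at stake is lurasidone exposure in a suicidal outpatient population, and protocol compliance at sites that notice the conflict and have to improvise.

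The documents show that the sponsor regards raised lurasidone exposure as a real risk. Appendix 1 bars nefazodone expressly as a CYP3A4 inhibitor and also excludes diltiazem and verapamil. Protocol 10.1 has participants avoid grapefruit because it can raise blood levels of drugs such as lurasidone. A class row has a precedent too: Appendix 1 bars drugs metabolized mainly by CYP2C8 for both episodic and chronic use.

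**Working it through.** **1. Dose levels against the limit.** Inputs are the morning and evening lurasidone doses in Protocol Tables 2 and 3 and the 40 mg/day limit in 15.3.1. Each printed daily total is reproduced, then divided by 40.

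| Dose level | Morning + evening (mg) | Daily total (mg) | Total / 40 | Within limit |
|---|---|---|---|---|
| Day 1 | 16.5 + 16.5 | 33 | 0.825 | yes |
| Maintenance | 33 + 33 | 66 | 1.65 | no |
| Up-titration step 1 | 33 + 66 | 99 | 2.48 | no |
| Up-titration step 2 | 66 + 66 | 132 | 3.30 | no |
| Down-titration step 1 | 16.5 + 33 | 49.5 | 1.24 | no |
| Down-titration step 2 | 16.5 + 16.5 | 33 | 0.825 | yes |

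After Day 1, only down-titration step 2 meets the limit.

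**2. Whether step 2 can be used for this purpose.** Under 10.3 it is available for somnolence and nothing else. The side-effects wording in 6.6 would still not cover a preventive reduction when an inhibitor is started. Step 2 also takes DCS from 950 to 700 mg/day in the NRX-101 arm only: 1 − 700/950 = 26%.

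**3. Whether the concomitant-drug rules keep the inhibitors out.** Appendix 1 read row by row:

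- *Barred by name:* for example ketoconazole, itraconazole, erythromycin, clarithromycin, diltiazem, verapamil, nefazodone, cimetidine and eight protease inhibitors.
- *Closed by class row or allow-list:* antianginals and antiarrhythmics are not allowed at all. Antivirals are limited to listed agents. Systemic antifungals are not allowed for episodic use. Antineoplastics are not allowed episodically and need Medical Monitor approval for chronic use.
- *Left open apart from named drugs or subclasses:* antibiotics (episodic and chronic), antihypertensives (chronic) and antidepressants (chronic).

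A moderate inhibitor in the third group falls under the permissive default in 15.3.1.

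**4. Cost of excluding the class.** 15.3.1 says "Participants requiring excluded medications will be discontinued from the study" and 9.1.3 says "Participants who discontinue from the study will not be replaced". The power check uses a two-sample t-test with effect size d = 0.66 (the planned value) and two-sided alpha 0.05. The noncentrality is d / √(1/n₁ + 1/n₂) on n₁ + n₂ − 2 degrees of freedom. The number lost is an assumption, with all data from those participants treated as lost.

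| Lost entirely (assumed) | n₁ / n₂ | Noncentrality | Power |
|---|---|---|---|
| 0 | 37 / 37 | 2.839 | 80.0% (the plan's figure) |
| 1 | 36 / 37 | 2.819 | 79.4% |
| 2 | 36 / 36 | 2.800 | 78.9% |
| 4 | 35 / 35 | 2.761 | 77.7% |

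**The case against.** The best defence is that the text already implies the answer. The 40 mg/day sentence stands in the same section as the permissive default, and a specific limit normally overrides a general permission. With the dose fixed at 66 mg/day and no interaction-driven decrease allowed, the only way to comply is not to co-administer. A site can indeed do that, by withholding the inhibitor or not enrolling the patient. But nothing instructs it, and the explicit rule is that a drug not specifically excluded is allowed. A safety limit should not depend on each site working through that inference.

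A second objection is that the documents never say which drugs are moderate inhibitors, so the affected group cannot be shown to be large, or even counted. That stands, and it limits the size of the point.

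Three stronger readings are tempting, and the documents do not support them:

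- *Every moderate inhibitor not named in Appendix 1 is allowed.* Class rows and allow-lists bar some unnamed drugs. Systemic antifungals are a poor example of the gap: episodic use is barred, and the permission for chronic use can be read only in the SAP copy, because that cell is missing from the Protocol text available here.
- *An affected participant exceeds the limit on 41 of the 42 treatment days.* That count (Days 2 to 42) assumes the inhibitor is taken throughout. The limit applies only while both drugs are taken, so a short course counts only for its own days.
- *The primary inference is compromised.* Nothing here changes Type I error, the planned sample size or the analysis model.

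**Conclusion.** The inconsistency is real and goes beyond missing detail: the stated dosing and concomitant-drug rules, followed together, can breach the protocol's own limit. Its reach is confined to moderate CYP3A4 inhibitors in classes that Appendix 1 leaves open. On each day such a drug is taken at the maintenance dose, lurasidone is 65% above the limit; at the first down-titration step it is 24% above. The number of participants affected is unknown and may be small.

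The conclusion rests on reading the 40 mg/day sentence as an instruction, which its position in the concomitant-medication section supports, and on at least one moderate inhibitor falling in an open class, which the documents alone cannot confirm. The change should be made on safety grounds, because it is specific and inexpensive.

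**What to change.** In Protocol 15.3.1, keep the 40 mg/day sentence as the rationale and add directly after it: *Because the study maintenance dose is 66 mg/day, moderate CYP3A4 inhibitors are not allowed from randomization through Day 42 (see Appendix 1).*

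In Protocol Appendix 1, add the row: *CYP3A4 inhibitors, moderate: episodic N, chronic N.* State there that a patient whose maintained antidepressant belongs to this class is ineligible rather than washed out. This respects the reason 15.3.1 gives for holding antidepressants stable, "to prevent withdrawal symptoms that may occur if such drugs are rapidly discontinued". Sites will need a reference list of the class, since the documents contain none.

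Align SAP 12.3.1 and SAP Appendix 1 for consistency only; the SAP does not govern what sites do. Leave Section 10.3 and the titration tables as they are. A compulsory 33 mg/day path would meet the limit, but it would reduce DCS in one arm only.

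**Cost.** Eligibility becomes slightly narrower. More seriously, a participant who needs even a brief course of such a drug must be discontinued, with an Early Termination Visit and no replacement. In this population that is a clinical cost as well as a statistical one. The 77.7% power for four participants lost is a worst case for that number, because visits before discontinuation would ordinarily still contribute to the MMRM.

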15.3.2 Concomitant Therapy

Participants receiving concurrent psychotherapy that has been stable in type and frequency (e.g., weekly, monthly) for at least 3 months prior to Screening are eligible for study entry if the psychotherapy is expected to remain stable for the duration of the patient's participation in the study. Any changes in psychotherapy type and/or frequency during the study should be discussed with the Medical Monitor as soon as the investigator is aware of the proposed change.

15.3.3 Alcohol Restrictions

Participants should not use alcohol during the study. Ethyl alcohol may increase the possibility and risks of seizures in participants with a history of alcoholism receiving cycloserine.

15.3.4 Positive Drug Screen

Participants who have a positive urine drug screen two times in a row for use of any cocaine, opiates and non-prescribed amphetamine and non-prescribed barbiturates will be withdrawn from the study.

15.4 Laboratory/Diagnostic Procedures

Clinical laboratory safety testing will be performed locally at the study site using a Clinical Laboratory Improvement Amendments (CLIA)-certified laboratory. The frequency and type of procedures are detailed in the Schedule of Assessments (Table 1). Local laboratory normal ranges must be reported according to gender.

Participants will have their blood drawn for clinical chemistry (ALT, AST, GGT, ALK phosphatase, Creatinine, T4, T3,TSH, Albumin, BUN, Calcium, Sodium, Potassium, Chloride, Glucose, Total Bilirubin, Direct Billirubin, Total Protein, Total Cholesterol, HDL/LDL, Triglycerides, Uric Acid, HbA1c) and hematology testing (Red blood cell count, White blood cell count, Platelet count, Hemoglobin, Hematocrit, Neutrophils Absolute or percent, Lymphocytes Absolute or percent, Monocytes Absolute or percent, Eosinophils Absolute or percent, Basophils Absolute or percent). Urine sample testing for pregnancy and drug screen will be by dipstick. In the event of clinically significant abnormal laboratory test result(s), follow-up laboratory testing may be conducted, at the discretion of the investigator. If applicable, clinically significant changes from baseline in laboratory results will be noted as AE(s), in accordance with Section 15.2.1.

15.5 Physical Examinations, Vital Signs, Height, and Weight

Physical examinations, vital signs, height, and weight will be obtained at the noted visits. Vital signs (blood pressure and heart rate) may be repeated 15 min apart, as needed, in order to obtain a resting reading. If applicable, clinically significant changes from baseline in physical examination parameters, vital signs, and weight will be noted as AE(s), in accordance with Section 15.2.1.

15.6 Electrocardiograms

Twelve-lead ECGs will be obtained after the patient has been resting in a semi-recumbent position for at least 5 minutes. All digital ECGs will include the date and time obtained, heart rate, QRS duration, PR interval, RR interval, QT interval, and QTcF interval using Fridericia formula (Puddu et al., 1988). If indicated, additional ECG assessments may be performed, at the discretion of the investigator. If applicable, clinically significant changes from baseline in ECG assessments will be noted as AE(s), in accordance with Section 15.2.1.

15.7 Study Monitoring by the Drug Safety Monitoring Board (DSMB)

The study will be monitored for safety, futility, and efficacy by a DSMB. Interim analysis for safety will be conducted six weeks after the first 30-35 participants complete Day 42 based on reported Adverse Events and Serious Adverse Events. The study may be stopped for safety concerns. A second DSMB assessment for safety and futility will be conducted when 45-50 participants have reached day 42.

16. STATISTICS

The study analyses will be conducted in a GCP environment (ICH E6 and E9 [R1]). All analyses will be pre-specified in a Statistical Analysis (SAP) and finalized prior to database lock. If the methods in the SAP do not agree with this protocol, the methods described in the SAP will govern the analysis.

16.1 Randomization

Randomization will be stratified by evidence of a suicidal event in the prior 12 months (none, any).

16.2 Study Populations

The study includes prospectively defined study populations. The Intent to Treat (ITT) population will include all participants who received at least one dose of the oral treatment and had any post–randomization efficacy assessments. The modified ITT (mITT) population will include the ITT population with at least one post-baseline efficacy observation; the mITT population will also exclude subjects with a major protocol deviation, e.g. ineligibility, unreliable MADRS-10 scoring, proscribed treatment. The Per Protocol (PP) population will include the subset of ITT participants who were eligible, who have any post–randomization efficacy assessments within one day of scheduled visits through Day 7 and within three days of scheduled visits through Day 42, and who had no major protocol violations. The Safety population will include all participants as treated with study treatment and with any post–randomization safety data.

The mITT population will be used for the primary analyses for efficacy. If <5 percent are to be excluded from the ITT population, then the analysis will not be performed for the PP population.

Protocol violations will be reviewed in real time and prospective rules will be set for exclusions from the PP population. A Biostatistics Data Review Meeting (BDRM) will be held to identify all major protocol deviations prior to database lock inclusive of any case exclusions from the mITT and PP population as well as to censor any efficacy data following proscribed treatments.

